9.0 Confidentiality, Privacy and Data Management

See the Research Data Plan Review Form.

9.1 Confidentiality

9.1.1 Identifiers associated with data and/or specimens

See the Research Data Plan Review Form.

9.1.1.1 Use of Codes, Master List

See the Research Data Plan Review Form.

9.1.2 Storage of Data and/or Specimens

See the Research Data Plan Review Form.

9.1.3 Access to Data and/or Specimens

See the Research Data Plan Review Form.

9.1.4 Transferring Data and/or Specimens

N/A

9.2 Subject Privacy

See the Research Data Plan Review Form.

10.0 Data and Safety Monitoring Plan

10.1 Periodic evaluation of data

The study coordinator and the PI will be responsible for the daily oversight of subject safety. Medical history will be reviewed by the study staff, and based on eligibility criteria, any questionable medical histories will be brought to the attention of the medical monitor for final inclusion determination prior to randomization. In a similar manner, contraindications for the treatment products and vital signs will be checked by study staff at each in person visit. The medical monitor will be available via phone for any consultations as necessary.

Subjects will be under medical supervision while in the study (i.e., by the medical monitor) and seen on an ongoing basis by our research staff who will document adverse events. The medical monitor will assess all adverse events and will be available for consultation over the phone for urgent matters. Otherwise, the PIs and/or the medical monitor will meet weekly with the study staff to review patient's progress and their experiences with the study products, including any adverse events.

10.2 Data that are reviewed

Data that will be reviewed include:

- Accrual and retention
- Medical history and concomitant medications
- Adverse events and serious adverse events
- Protocol deviations/violations

10.3 Method of collection of safety information

All data, including safety data, will be coded directly into REDCap electronic case report forms during study visits. Participant adverse events and serious adverse events will be assessed at each in-person study visit and each phone call visit but can be reported at any time during the study.

10.4 Frequency of data collection

Safety data, including adverse events and serious adverse events will be collected at each study contact.

10.5 Individuals reviewing the data

The study coordinator and the PI will be responsible for the daily oversight of subject safety. The PI and/or the medical monitor will meet weekly with the study staff to review patients' progress and their experiences with the study products, including any adverse events. For more urgent and/or serious adverse events, the medical monitor will be available for consultation by phone. The medical monitor will then make any needed medical recommendations and a determination regarding whether the participant is able to continue with the study.

10.6 Frequency of review of cumulative data

All of the data from the study (including adverse events) will be reviewed by the leadership group, including [name], on a regular basis to review patients' progress and their experiences with the study products.

10.7 Statistical tests

Statistical methods will be used to analyze the safety data to determine whether harms are occurring. Paired sample t-test (or nonparametric Wilcoxon Rank-Sum test) will be used to examine the changes in the outcome measures (CPD, CO, subjective measures, BP, HR) from the baseline.

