7.0 Study Design and Procedures

7.1 Study Design

This is a randomized, double-blind, placebo-controlled, parallel-group study that will occur in three phases over 7 weeks.

Time & Events Table								
	Baseline	Pre-Cessation			Cessation			
Study Week Number	-1	0	1	2	3	4	5	6
Study Visit Number	1	2	Ph #1	3	Ph #2	4	Ph #3	5
Study Day Number	-7	0	7	14	21	28	35	42
MEASURES								
Screener 3	X							
Concomitant medications	X	X	X	X	X	X	X	X
Medical history	X							

NIDA Quick Screen	X						
Cigarette details	X						
Adverse events		X	X	X	X	X	X
Daily cigarette/film diary collection		X	X	X	X	X	X
Demographics	X						
Tobacco Use History	X						
Environmental Tobacco Smoke Questionnaire		X		X		X	X
Cigarette Evaluation Scale		X	X	X	X	X	X
Nicotine dependence		X		X		X	X
Minnesota Withdrawal Scale		X		X		X	X
Questionnaire Smoking Urge		X		X		X	X
Perceived Stress		X		X		X	X
Confidence to quit		X		X		X	X
Study product side effects			X	X	X	X	X
Study product evaluation			X	X	X	X	X
Likelihood of Use Scale				X		X	X
Dose Awareness							X
BIOMEASURES							
Height		X					
Weight		X		X		X	X
Waist/Hip ratio		X					X
Exhaled CO	X	X		X		X	X
Blood pressure & pulse	X	X		X		X	X
Pregnancy test	X			X		X	

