8.2 Sample size determination

Previous studies have shown the effects of NRT on cessation in sample sizes that are comparable to (e.g., [name], et al., 1992; Rose, et al., 1998; Rose, et al., 2006) the one proposed here (n=15 per treatment arm). Based upon such work, we are confident that we will have sufficient power to achieve the aim of the proposed research.

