8.3 Statistical methods

Paired sample t-tests (or nonparametric Wilcoxon Rank-Sum tests) will be used to examine changes in the outcome measures (CPD, CO, subjective measures, BP, HR) from baseline.

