11.0 Risks

Potential risks for subjects are minimal. We have previously tested both single and repeat administration of each of the nicotine film doses which will be dispensed to subjects. We found that they were well-tolerated by subjects and produced nicotine levels in the blood that are less than subjects routinely receive from their cigarette smoking.¹⁹ Subjects will have a review of their medical history prior to entry into the study. Subjects will be under medical supervision throughout their participation in the study, and adverse symptoms will be recorded by the research staff and monitored by the medical monitor and PIs. The major risks associated with the study are related to the use of nicotine (which is similar to the nicotine received from smoking) and nicotine withdrawal.

Additional potential risks include:

- **Nicotine film side effects:** Excess nicotine can cause mild symptoms such as nausea, dizziness, diarrhea, rapid heartbeat, heartburn, and hiccups. Occasionally these symptoms are more severe (e.g., vomiting) such as when an individual receives more nicotine than they are accustomed to. This, however, is unlikely to occur with the doses used in this study.
- **Nicotine withdrawal symptoms:** Ceasing conventional cigarette use may result in nicotine withdrawal symptoms (e.g., irritability, anxiety, restlessness, depressed mood, increased appetite, fatigue, difficulty concentrating). These symptoms will be monitored at each visit. Those receiving placebo films may experience more serious nicotine withdrawal symptoms.
- **Risk to fetus and breast fed infants:** Nicotine is known to be harmful to the developing human fetus, either from cigarettes or at the dose being used in this study. Women who are pregnant or are nursing a child may not participate in this research study. Women capable of becoming pregnant will be administered a pregnancy test prior to beginning the research. Participants must agree to take reasonable and necessary precautions against becoming pregnant during the period of the investigation.
- **Loss of confidentiality:** There is a risk of loss of confidentiality if information is obtained by someone other than the investigators. Precautions will be taken to prevent this including direct coding of data in REDCap.
- **Randomization:** Participants will be assigned to a treatment program by chance. The research intervention they receive may prove to have more side effects than the other research intervention(s).

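### The statistical safety analysis tests only within-person change and plans no by-arm summary of adverse events or side effects, so it cannot separate a nicotine or regimen effect from changes common to all arms.

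*Combined protocol and SAP*

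**What the plan says.** The design in 7.1 supplies a concurrent control: "This is a randomized, double-blind, placebo-controlled, parallel-group study". Section 8.2 gives "n=15 per treatment arm", and 8.1 gives 45 randomized in total.

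Safety information is gathered throughout. Section 10.4 states: "Safety data, including adverse events and serious adverse events will be collected at each study contact". Section 1.3 makes side effects a secondary endpoint.

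Section 10.7 sets the aim of the safety statistics: "Statistical methods will be used to analyze the safety data to determine whether harms are occurring". The one method that follows is a paired t-test, or a Wilcoxon Rank-Sum test as the nonparametric option, which "will be used to examine the changes in the outcome measures (CPD, CO, subjective measures, BP, HR) from the baseline". Section 8.3, the only other statistical methods text, says the same tests "will be used to examine changes in the outcome measures (CPD, CO, subjective measures, BP, HR) from baseline". Neither section mentions adverse events, serious adverse events or a contrast between arms, and no other section plans a by-arm table of them.

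Other safety provisions are clinical: weekly review by the PI and/or medical monitor (10.5), regular cumulative review by the leadership group (10.6), a causality judgment on each event (19.3), and safety reports that weigh a new reaction against earlier similar ones (19.4.1).

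**The concern.** The method does not match the aim stated for it. Cigarettes per day and CO are efficacy measures and say nothing about harm from a nicotine film. Adverse events, the most direct evidence of harm, are not analysed. Blood pressure and heart rate are relevant, but a change from baseline within a person has no control.

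The protocol expects symptoms that do not come from nicotine in the films. Section 11.0 warns: "Those receiving placebo films may experience more serious nicotine withdrawal symptoms". The same section tells participants that one assigned treatment may turn out to have more side effects than another. That is a between-arm question, and no planned analysis addresses it. The random regimen (0 and 4 mg films, with daily totals of 4, 8 or 12 mg) and the steady regimen (four 2 mg films) differ in pattern at the same average daily dose (7.4.2). A harm specific to the random pattern can be seen statistically only by comparing arms.

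**Working it through.** The documents give no safety event rate, SD, effect size or alpha, so there is no safety figure to reproduce. The sample size is consistent: 3 × 15 = 45. The shift sizes, event rates and two-sided alpha of 0.05 below are assumptions for illustration.

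**1. What change from baseline contains at each visit**

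| Change | Smoking instruction | What is mixed together |
|---|---|---|
| Visit 2 to Visit 3 | Keep smoking as usual (7.2.2.8) | Nicotine or regimen effect, plus anything else that moves over two weeks; no control |
| Visit 2 to Visits 4 and 5 | Stop the morning after Visit 3 (7.2.4.7) | The same, plus stopping smoking and withdrawal |

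**2. A shift shared by all arms, with no nicotine effect**

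Let the shift be d SDs of the change score. The paired t statistic is then noncentral t with n − 1 degrees of freedom and noncentrality d√n. For n = 15 and d = 0.5, for example, the noncentrality is 0.5 × √15 = 1.94.

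| Shift d | Paired test, one arm of 15 | Paired test, all 45 | Between-arm test |
|---|---|---|---|
| 0.3 | 19% | 50% | 5% |
| 0.5 | 44% | 91% | 5% |
| 0.8 | 82% | 99.9% | 5% |
| 1.0 | 95% | about 100% | 5% |

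Both paired columns are shown because the plan does not say whether the test is run per arm or pooled.

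The reverse error is also possible. If nicotine raises heart rate by δ and stopping smoking lowers it by δ, the mean paired change in a nicotine arm is δ − δ = 0. A placebo arm that quits to the same extent changes by −δ, so the between-arm difference is 0 − (−δ) = δ and remains visible.

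**3. Side effects have no paired change**

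Films are first dispensed at Visit 2, after randomization (7.2.2.6). Side effects of the study product therefore have no pre-film value. Even if subjective measures were read to include them, the test in 10.7 could not be applied.

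**4. What by-arm reporting could deliver at this size**

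- Exact (Clopper-Pearson) two-sided 95% upper limit for 0/15: 1 − 0.025^(1/15) = 21.8%. The one-sided 95% bound is 1 − 0.05^(1/15) = 18.1%.
- Exact two-sided 95% interval for 3/15 (20%): 4.3% to 48.1%.
- Fisher exact power, 15 v 15: 15% for true rates of 10% v 30%, and 54% for 10% v 50%. With both nicotine arms pooled against placebo (30 v 15): 25% and 76%.
- Blood pressure or heart rate difference detectable with 80% power: 1.06 SD at 15 v 15, and 0.91 SD at 30 v 15.

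These figures reflect the sample size, not the choice of test. They show that the replacement should be estimation and that an arm with no events cannot be called safe.

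**The case against.** The strongest reply is that harm detection does not rest on 10.7. Events are asked about at every contact, reviewed weekly and cumulatively, and judged individually for causality. This stands. A reader might infer that the trial cannot detect harm at all, and the documents do not support that. The gap is confined to the planned statistics. The clinical reviews are not arm comparisons, however, and do not supply the analysis that 10.7 promises.

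Two other inferences go too far. One is that every blood pressure or heart rate change is confounded by quitting. The Visit 3 measurement precedes the quit instruction, so that change is uncontrolled but free of this particular mixture. The other is that changes would be attributed to the films. Section 10.7 says only that changes will be examined and gives no attribution rule.

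It could be said that the Rank-Sum test, a two-sample method, implies an arm comparison. The sentence names no groups and offers it as the alternative to a paired test, so it is better read as a mislabel of the signed-rank test.

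Arm contrasts also have limits. All arms receive films, and the placebo film lists the same excipients in somewhat different amounts (7.4.1), so the contrasts do not isolate harms of the film base, such as the mouth irritation noted in 11.0. At Visits 4 and 5 the arms may differ in quitting, which is the trial's own hypothesis, so a contrast there is a total effect that includes quitting and withdrawal.

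Finally, the missing arm contrast for blood pressure and heart rate is the same gap as in 8.3 and should be counted once. The absence of any adverse event or side-effect summary is the distinct part.

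**Conclusion.** The concern holds for the statistical analysis. As written, it omits adverse events, serious adverse events and side effects and never uses the placebo arm. It therefore cannot separate an effect of nicotine or of the random regimen from changes common to all arms. Under assumed common shifts of 0.3 to 1.0 SD with no nicotine effect, the paired test in one arm would be significant in 19% to 95% of trials. The size of any real shift is unknown.

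This should be changed, but it does not invalidate the trial: the data are already scheduled for collection, and case-level safety review is in place. The change would make the comparison valid but not precise, since 15 per arm leaves wide intervals.

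**What to change.** Put the safety analysis in 8.3 as final reporting after unblinding, and replace the method sentence in 10.7 with a cross-reference. Keeping by-arm tables out of ongoing monitoring protects the blinding of researchers in 7.4.5. Specify:

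- By-arm counts and proportions, with two-sided exact 95% intervals, of participants with any adverse event, a film-related adverse event, a serious adverse event, withdrawal due to an adverse event, and each listed side effect.
- Between-arm differences with 95% intervals for random v placebo, steady v placebo, both nicotine arms v placebo, and random v steady.
- Blood pressure and heart rate compared between arms, adjusted for the Visit 2 value, separately at Visit 3 and at Visits 4 and 5.
- A statement that Visit 4 and 5 contrasts are total effects including differences in quitting and withdrawal, and that no arm contrast isolates harms of the film base.
- A statement that the results are estimates, and that an absence of events or of significance is not evidence of safety at this size.

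The cost is revised wording and a few more tables, with no new data or visits. The downside is that many intervals will be wide.

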8.0 Subject Numbers and Statistical Plan

8.1 Number of Subjects

Participants will be enrolled in the study until a total of 45 are randomized. We anticipate that we will need to enroll up to 70 participants in order to randomize 45.

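### Section 10.7 sets out to detect harm using only a test of change from baseline, with no confidence interval and no comparison with placebo

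*Combined protocol and SAP*

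**What the plan says.** Section 10.7, in the data and safety monitoring plan, opens with the aim: "Statistical methods will be used to analyze the safety data to determine whether harms are occurring". The method follows in one sentence: "Paired sample t-test (or nonparametric Wilcoxon Rank-Sum test) will be used to examine the changes in the outcome measures". The measures listed are cigarettes per day, exhaled CO, subjective ratings, blood pressure (BP) and heart rate (HR). Section 8.3 gives the same method for the trial as a whole.

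Section 10.7 gives no significance level or sidedness, no confidence interval and no contrast with placebo. It does not say whether the test is run within each arm or on pooled data, or how a non-significant result will be read.

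The size of the trial comes from section 8: "Participants will be enrolled in the study until a total of 45 are randomized", with "n=15 per treatment arm". Section 8.2 asserts adequate power ("we are confident that we will have sufficient power to achieve the aim of the proposed research"), but gives no figure, and the assertion concerns the study's aim, not safety.

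The Time & Events Table in 7.1 schedules BP and pulse at all five in-person visits. Visits 1 and 2 precede the first film, Visit 3 ends two weeks of film use with unrestricted smoking, and Visits 4 and 5 follow the quit date.

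**The concern.** There are two separate problems.

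The first is attribution. Between Visit 2 and Visit 5 a participant starts the films, keeps smoking for two weeks and is then told to stop. A change from baseline within an arm mixes the film with stopping smoking, withdrawal and the passage of time. The trial has a placebo arm that goes through the same sequence, and 10.7 does not use it.

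The second is how the result is read. A test of no change can flag a rise, but failing to reject does not show that there was none. In a small arm, non-significance is a common result even when a moderate rise is real. Since 10.7 offers no estimate or interval, the p-value is all a reader would have.

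This matters because a mean shift in BP or HR is a harm that the protocol itself makes plausible. Section 2.2 cites a human study in which uncontrollable delivery of cocaine raised mean systolic and diastolic pressure, and uses it to support random delivery. Section 11.0 lists rapid heartbeat among the effects of excess nicotine.

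**Working it through.** **Inputs from the plan.** 15 per arm (8.2) and 45 in total (8.1): 3 × 15 = 45, which agrees. Section 3.3.2 replaces only withdrawals before randomization, so an arm can end with fewer than 15 paired values. The plan gives no power figure for safety, so there is none to reproduce.

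**Assumptions, not in the plan.** Two-sided alpha 0.05; normally distributed changes; a true mean rise of d = 0.5 SD of the change score.

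**Formula.** For n paired changes, t has n − 1 degrees of freedom and noncentrality d√n. Power is the probability that |t| exceeds the critical value, and the miss rate is 1 − power. For 15 v 15 the noncentrality is d√(15/2), with 28 degrees of freedom.

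| Test | Noncentrality | Critical t | Power | Missed |
|---|---|---|---|---|
| One arm, n = 15 | 0.5√15 = 1.936 | 2.145 | 43.8% | 56.2% |
| One arm, n = 12 | 0.5√12 = 1.732 | 2.201 | 35.3% | 64.7% |
| Both active arms pooled, both shift, n = 30 | 0.5√30 = 2.739 | 2.045 | 75.4% | 24.6% |
| All 45 pooled, all shift equally | 0.5√45 = 3.354 | 2.015 | 90.7% | 9.3% |
| Active v placebo, 15 v 15 | 0.5√7.5 = 1.369 | 2.048 | 26.2% | 73.8% |

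A simulation of 400,000 trials gave 56.1% for the first row.

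**Sensitivity of the 56%.**
- Effect size (n = 15, two-sided): 89% missed at 0.2 SD, 81% at 0.3, 18% at 0.8 and 5% at 1.0.
- One-sided 5% at 0.5 SD: 42% missed.
- If 0.5 SD is on the scale of the measurement rather than the change, the effect on the change scale is 0.5/√(2(1 − ρ)). The miss rate is then 67%, 56%, 36% and 19% for baseline–follow-up correlations ρ of 0.3, 0.5, 0.7 and 0.8.
- Signed-rank test: about 59% missed. Section 10.7 names the rank-sum test, which is for independent samples; signed-rank is its paired counterpart.
- All 45 pooled: the 9% requires placebo to rise as much as the active arms, which would not be a film effect. By simulation, the miss rate is 43% if only the two active arms shift and 82% if only one does.

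**What an interval would show.** One-sided 95% half-widths in SDs of the change:
- within an arm of 15: t(0.95, 14)/√15 = 1.761/3.873 = 0.45;
- active minus placebo, unadjusted: t(0.95, 28) × √(2/15) = 1.701 × 0.365 = 0.62.

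The two-sided 95% half-widths are 0.55 and 0.75.

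**Illustration in units.** If the SD of the change in systolic BP is 10–12 mmHg (an assumption; the plan gives none), 0.5 SD is 5–6 mmHg and 0.62 SD is about 6.2–7.4 mmHg. For HR with an assumed SD of 8–10 bpm, they are 4–5 bpm and about 5.0–6.2 bpm.

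**The case against.** The strongest reply is that no stated action depends on this test. The medical monitor assesses all adverse events (10.1), reviews abnormal findings weekly (19.3), decides on individual continuation (10.5) and can set stopping rules (10.8). Staff check vital signs at each in-person visit (10.1), all study data are reviewed cumulatively (10.6), and related serious or unexpected events go to the IRB (19.7). All of that stands, so it would be wrong to infer that safety rests on the p-value alone. These sections do not, however, specify a group-level estimate for BP or HR, and a moderate mean shift spread across an arm need not appear as anyone's adverse event.

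A reader might also infer that the team would treat p > 0.05 as a finding of no harm. The documents do not say so. They give no threshold and no rule of interpretation; the text leaves that reading open and goes no further.

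Nor does the plan support an unconditional 56%, since it does not specify per-arm testing, alpha or sidedness. It would also be one-sided to say that the error always favours the product: an uncontrolled change can produce a false signal of harm as easily as it can hide a real one.

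Finally, a formal margin for excluding a rise would fit poorly here. Even with a true change of zero, a one-sided 95% bound within an arm of 15 falls below 0.5 SD only 58% of the time. That objection is accepted, and no margin is proposed.

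**Conclusion.** The point holds in a limited form. Section 10.7 gives statistics the task of finding harm, but supplies only a test of change, without an interval and without the placebo contrast that the design makes available. The attribution problem needs no numerical assumption. The risk of misreading non-significance is a matter of degree: about 56% of true 0.5-SD rises missed per arm with 15 completers at two-sided 5%, 65% with 12, and 25% if both active arms are pooled and both shift. The effect size, alpha and unit of analysis are assumptions.

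Replacing the within-arm test with a between-arm p-value would solve attribution but not interpretation, because the miss rate at 15 v 15 is 74%. The estimate and its interval are what the section lacks. The conclusion stops short of saying that the trial will misreport safety or that its clinical monitoring is inadequate.

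**What to change.** In 10.7, for the final unblinded analysis, report for systolic BP, diastolic BP and HR:
- the mean change in each arm, with a confidence interval;
- the baseline-adjusted difference of each active arm from placebo, with a confidence interval;
- both at Visits 3, 4 and 5, with one visit named in advance as the main safety comparison, and with a statement of which pre-film reading (Visit 1 or Visit 2) is the baseline.

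Add one sentence saying that a non-significant test will not be described as absence of harm. No exclusion margin is required. Confining the arm comparison to the final analysis leaves the blinding in 7.4.5 untouched.

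Naming one visit matters because three measures × (three arms + two differences) × three visits gives 45 intervals. At a single visit there are 15, of which 3 × 2 = 6 are comparisons with placebo.

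The cost is a few sentences and one table from data already scheduled, with no extra participants or visits. The drawback is wide intervals at about 15 per arm, so many safety results will have to be reported as inconclusive.

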- 7.2.1.10** Participants will be instructed to continue smoking their usual brand of cigarettes for the next week, to avoid using any other tobacco products, and to maintain a daily diary of cigarette use on which they will record the number of cigarettes they smoke each day.
- 7.2.1.11** Participants will be compensated for completing the study visit and procedures.

7.2.2 Pre-Cessation Phase – Visit 2 [1 week after Visit 1] (Day 0 -1/+3 days)

- 7.2.2.1** Adverse events will be documented.
- 7.2.2.2** The cigarette daily diary will be reviewed and recorded by the researcher to confirm that the participant completed their diary, that ≥ 10 cigarettes were smoked on at least 5 out of the last 7 days, and that no quit attempts have been reported. If any of these criteria have not been fulfilled, the participant will be excluded from randomization, and the End of Trial Form will be completed.
- 7.2.2.3** Use of other tobacco products in the past 7 days will be assessed. If the participant has used any other tobacco product in the past 7 days, they will be excluded from randomization, and the End of Trial Form will be completed.
- 7.2.2.4** Concomitant medications will be assessed to confirm participants have not initiated nicotine replacement therapy or cessation medication use since Visit 1. If they have initiated either of these medication categories, they will be excluded from randomization, and the End of Trial Form will be completed.
- 7.2.2.5** Participants who meet all eligibility criteria for randomization will complete the measures and study procedures indicated on the Time & Events Table for the visit.
- 7.2.2.6** Following randomization, subjects will receive their assigned study products. Research staff will explain how to use the nicotine films and provide participants with administration and dosing instructions. Participants will receive a 14-day plus 3-day supply of the assigned film regimen (68 films total). The films will be packaged and numbered so they are taken in a specific, sequential order throughout each day. Participants will be instructed to take one film every 3-4 hours each day for a total of 4 films per day.
- 7.2.2.7** Participants will be asked to return all used (opened/empty) and unused (unopened) study product pouches at their next study visit.
- 7.2.2.8** Participants will be instructed to continue smoking their usual brand of cigarettes ad libitum over the next two weeks and to avoid using any other tobacco products.

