7.2.4 Cessation Phase – Visit 3 (Day 14 ± 3 days)

At this in-person visit, the following procedures will be conducted:

- 7.2.4.1** Adverse events will be documented, and any concomitant medication changes will be recorded.
- 7.2.4.2** The daily cigarette/film diary will be collected and recorded by the researcher. Use of other tobacco products in the past 7 days will also be assessed.
- 7.2.4.3** Participants will complete the measures and study procedures indicated in the Time & Events Table.
- 7.2.4.4** All nicotine pouches from the previous weeks (unopened, opened, or empty) will be collected by the researcher.
- 7.2.4.5** Participants will be provided with a new supply of their assigned nicotine films (14-day plus 3-day supply [68 films total]) to use over the next two weeks until their next study visit.
- 7.2.4.6** Participants will be asked to return all used (opened/empty) and unused (unopened) study product pouches at their next study visit.
- 7.2.4.7** Participants will be instructed to cease all cigarette use and to only use their assigned nicotine films beginning the next morning.
- 7.2.4.8** Participants will be provided with the document from the Centers for Disease Control and Prevention titled, "A Report of the Surgeon General: How Tobacco Smoke Causes Disease." Participants will also be given a document with tips to prepare and succeed in a quit attempt.
- 7.2.4.9** Participants will be instructed to continue to maintain a daily diary of their nicotine film use. This diary will require that they record the time of day each film was taken. Participants will be instructed to only record cigarettes smoked on their diary in the event that they experience a slip.
- 7.2.4.10** Participants will be compensated for completing the study visit and procedures.

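### The safety test in 10.7 (same method in 8.3) is a paired change from baseline with no arm comparison and no stated visit, so it cannot attribute a change to the films

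*Combined protocol and SAP*

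**What the plan says.** Section 10.7 opens with its purpose: "Statistical methods will be used to analyze the safety data to determine whether harms are occurring". It then names a single method, a paired t-test or Wilcoxon rank-sum test that "will be used to examine the changes in the outcome measures (CPD, CO, subjective measures, BP, HR) from the baseline". Section 8.3, the whole of the statistical methods, says that the same tests "will be used to examine changes in the outcome measures (CPD, CO, subjective measures, BP, HR) from baseline". No other section adds an analysis that compares arms.

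The design could support one. Section 7.1 states: "This is a randomized, double-blind, placebo-controlled, parallel-group study". Section 8.2 gives 15 participants per arm. In the Time & Events Table, the row "Blood pressure & pulse" is filled at all five in-person visits: two readings before any film (Visits 1 and 2) and three on film (Visits 3, 4 and 5). The row "Study product side effects" starts only at the Day 7 call.

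At Visit 2, section 7.2.2.8 says: "Participants will be instructed to continue smoking their usual brand of cigarettes ad libitum over the next two weeks". Section 7.2.4.7 sets the quit for the morning after Visit 3, so Visit 3 readings precede it even though the heading of 7.2.4 places that visit in the cessation phase.

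Safety oversight is described separately. Adverse events are asked about at every contact (10.3, 10.4), and the medical monitor reviews them weekly and judges causality (19.3).

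**The concern.** A paired test asks whether people changed. It does not ask why. In this trial a change in pulse or blood pressure could come from the film, the passage of time, repeated measurement, altered smoking while on film, quitting after Visit 3, or withdrawal. Section 11.0 lists rapid heartbeat among the effects of excess nicotine, and also says that withdrawal may be worse on placebo. A within-person change can therefore show a rise that the film did not cause, or hide one that it did. The concurrent placebo group is the design's means of removing whatever all arms share, and the plan does not use it for safety.

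The wording leaves further gaps. It does not say whether arms are tested separately or pooled, at which visit, or against Visit 1 or Visit 2. Adverse events are not among the measures listed in 10.7. Side-effect ratings begin after films are dispensed, so they have no earlier value to pair with.

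**Working it through.** The documents give no effect size, SD or significance level for this test, so there is no stated figure to reproduce. Every bpm value below is an assumption chosen to show how the method behaves.

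**Inputs from the documents.** Three arms of 15, 45 in total (8.1, 8.2), so 30 receive nicotine. Pulse is read on film at Visit 3 (before the quit) and at Visits 4 and 5 (after it).

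**Assumed inputs.** Film effect f = +3 bpm (range 1 to 5). Change shared by all arms s = −3 to +3 bpm. SD of change 8 to 10 bpm. Change in a quitter w = −6 bpm (size 4 to 8). Two-sided 0.05.

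1. **What the paired change estimates at Visit 3.**
   - Active arm, f + s: 3 − 3 = 0 to 3 + 3 = 6. Over the range of f: 1 − 3 = −2 to 5 + 3 = 8.
   - Pooled over 45, (30/45)f + s: 2 − 3 = −1 to 2 + 3 = 5. Over the range of f: −2.3 to 6.3.
   - Placebo, s: −3 to +3, with no film effect at all.
   - If s = 0, the active-arm paired change equals f and the problem disappears. Nothing in the plan shows that s is 0.

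2. **What the arm difference estimates at Visit 3.** Let d be the active-minus-placebo difference in pulse change due to different ad libitum smoking. The arm difference is (f + s + d) − s = f + d. The shared change cancels; d does not. With f = 3 the result is 3 + d, and it equals 3 only if d = 0.

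3. **False signals from the paired test.** Take f = 0 and s = 3. Noncentral t with n − 1 degrees of freedom and noncentrality √n × s/SD:

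| | SD 10 | SD 8 |
|---|---|---|
| One arm, n = 15 | 19.2% | 27.3% |
| Pooled, n = 45 | 50.3% | 69.2% |

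   In simulation with a shift common to all arms (0.25, 0.5 or 0.8 SD), a between-arm t-test on change rejects about 5% of the time.

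4. **A masked effect.** Suppose the film raises a measure by 0.8 SD and quitting lowers it by 0.8 SD equally in both arms. In simulation (15 per arm) the active-arm paired test rejects about 5% of the time, and the comparison with placebo rejects 56%.

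5. **After the quit.** With quit proportion q, and ignoring s, the active-arm change is f − q × |w|. At an assumed 30% quitting: 3 − 0.30 × 6 = 1.2 (range −1.4 to 3.8). At 7%: 3 − 0.07 × 6 = 2.58 (0.44 to 4.72). If 30% quit on active film and 7% on placebo, the arm difference is 3 − (0.30 − 0.07) × 6 = 1.62. It remains a valid comparison of assignments, but it now includes quitting.

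6. **Precision of the by-arm alternative (95% half-width).**

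| Contrast | Formula | In SD | At SD 8–10 bpm |
|---|---|---|---|
| Within one arm, n = 15 | 2.145/√15 | 0.55 | 4.4–5.5 |
| 15 vs 15 | 2.048 × √(2/15) | 0.75 | 6.0–7.5 |
| 30 vs 15 | 2.017 × √(1/30 + 1/15) | 0.64 | 5.1–6.4 |
| 12 vs 12 (assumed retention) | 2.074 × √(2/12) | 0.85 | 6.8–8.5 |
| 24 vs 12 (assumed retention) | 2.032 × √(1/24 + 1/12) | 0.72 | 5.7–7.2 |

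   For events, zero in 30 is compatible with up to 1 − 0.025^(1/30) = 11.6%, and zero in 15 with up to 1 − 0.025^(1/15) = 21.8%. As an example, 6/30 against 1/15 differs by 13.3 points (Newcombe −12.1 to 31.5).

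**The case against.** The strongest reply is that harm in this trial is not judged by this test. The medical monitor reviews each event for causality (10.5, 19.3), and there are provisions for withdrawal, unblinding and stopping (3.3.1.2, 19.6, 10.8, 19.7). That stands, and it limits the severity. It does not repair the analysis that 10.7 promises, and a modest group shift in pulse or blood pressure may never be recorded as an individual event. A reader should not infer that safety goes unmonitored. The gap is in the analysis, not in collection or oversight.

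Second, 10.7 sits in the monitoring plan, where staff are blinded (7.4.5). Change from baseline can be examined without treatment codes, and a table produced after database lock cannot do that job. This also stands, so the paired summaries should be kept and the by-arm table added.

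Third, the same sentence in 8.3 governs the primary measures, although the hypothesis in 1.1 compares arms. The safety point is one consequence of that wider gap, and one revision of 8.3 should deal with both.

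Fourth, the rank-sum test is a two-sample test, which might suggest a planned arm comparison. But the text applies it to change from baseline and names no groups, so it cannot be read that way.

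Finally, the arms are small. That is true, and it is a reason to report estimates with intervals and claim little from them. It is not a reason to prefer a narrower interval on a contrast that cannot answer the question.

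**Conclusion.** The concern holds. As written, the test in 10.7 cannot separate a film effect from time, repeat measurement, changed smoking, quitting or withdrawal, and the placebo arm plays no part in the safety analysis. This follows from the wording and the design. The bpm figures only illustrate it and rest on assumed effects and SDs.

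The documents do not support two stronger readings. The first is that the Visit 3 arm difference isolates the film. Section 2.2 reports a 14% fall in expired CO when patches were used while smoking, so ad libitum smoking may differ by arm before the quit. The contrast with placebo is a net effect of assignment at every visit: film plus any difference in smoking at Visit 3, with quitting and withdrawal added at Visits 4 and 5.

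The second is that the missing arm comparison matters more than separating the phases, because dilution is small at 7% quitting. Section 2.1 gives 7% as a low end for abstinence after nicotine replacement, not as a Day 42 rate in this trial. The calculation also gives no effect to people who cut down without stopping. At 30% the assumed +3 bpm falls to +1.2, so the 7% figure supports no ranking.

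Severity is minor to moderate, because adverse events are already reviewed case by case and 15 per arm would not resolve a 3 bpm effect under any analysis shown here.

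**What to change.** Keep the blinded change-from-baseline summaries in 10.7 for monitoring during accrual, and say that they are descriptive. Add to 8.3, with a cross-reference from 10.7, a final by-arm safety table produced after database lock:

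- **Columns:** random, steady state, placebo, and pooled active. Both active regimens average 8 mg a day (7.4.2: 4 × 2 mg in the steady-state arm), but the separate columns are still needed because their peaks differ.
- **Baseline:** Visit 2, stated as the safety baseline because it is the last reading before the first film. The protocol uses the baseline label for Visit 1, so this has to be written down.
- **First film to Visit 3:** adverse events by onset up to and including the Visit 3 day, side-effect ratings at the Day 7 call and Visit 3, and BP/pulse change from Visit 2 to Visit 3.
- **After the instructed quit:** adverse events by later onset, later side-effect ratings, and BP/pulse change from Visit 2 to Visits 4 and 5.
- **Results:** estimates by arm, arm differences and 95% intervals.
- **Smoking status by arm beside each period,** from both diary and exhaled CO. After Visit 3 the diary records only slips (7.2.4.9), so an unkept diary looks like abstinence.

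The cost is one table specification and one cross-reference, with no new data, visit or dose. The downside is width: half-widths of about 0.64–0.75 SD, and more with dropout. The text should say that the table describes harm and cannot rule it out, and that the second period reflects the instruction to quit, not actual abstinence.
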